#### 9.2 Adverse Events

All AEs will be coded by system organ class and Medical Dictionary for Regulatory Activities preferred term. A treatment-emergent AE (TEAE) is defined as an AE which starts after start of the first open-labelbrexpiprazole, or an AE continues from baseline and is worsening, serious, trial drug-related, or results in death, discontinuation, interruption or reduction of trial medication. The incidence of the following events will be summarized by descriptive statistics:

- TEAEs
- TEAEs by severity
- TEAEs potentially causally related to the trial drug
- TEAEs with an outcome of death
- Serious TEAEs
- TEAEs leading to discontinuation of the trial drug

All TEAEs will be presented in listings. The listings of death due to AEs, serious AEs, AEs leading to discontinuation of the trial drug, will also be provided.

### 9.3 Clinical Laboratory Data

Listings of pregnancy test results by subject will be provided.

#### 9.4 Vital Sign Data

Vital signs are taken at screening, baseline, Week 4, and Week8/End of Treatment of. Assessments will include blood pressure, heart rate, respiratory rate, and temperature. In

addition, body weight and BMI are measured at screening, baseline, and each visit. The mean changes from baseline in vital signs, body weight, and BMI will be summarized by summary statistics. The incidence of potentially clinically relevant vital sign abnormalities will be tabulated in incidence tables. Criteria for the potentially clinically relevant vital sign abnormalities are provided in Appendix 1. If vital sign assessments are repeated for the same visit, the last repeat values are used for production of summary tables. The potential clinically relevant vital sign abnormalities are also listed by subject.

#### 9.5 Physical Examination Data

Physical examination data will be presented in a listing.

### 10 Changes in the Planned Analyses

None.

#### 11 Conventions

#### 11.1 Trial Visit Windows

Study visit windows will be used to map visits using study day intervals. The derived study window variable will be named as WEEK and will be footnoted. In listings it will be listed along with the eCRF study visit. The visit window convention shown in Table 11.1-1 is applied to tables and listings for efficacy scales, including IDS-SR, PHQ-9, GAD-7, WHODAS2.0, SDS, CGI-S, and CGI-I. The visit window convention shown in Table 11.1-2 is applied to patient diary entries, including PGI-I and 'word of the day'. In each table, the variable "target day" is defined using the number of days since the 1st use of open-label brexpiprazole. The first day of using open-label brexpiprazole is defined as 'Day 1'.

Table 11.1-1 Study Day and Visit Windows for Efficacy Scales (IDS-SR, PHQ-9, GAD-7, WHODAS2.0, SDS, CGI-S, and CGI-I) Target Daya Week Study Day Interval a 2 14 2~20 28 21~41 42-70b 56

<sup>b Evaluations occurring more than seven days after the last open-label brexpiprazole date will be excluded.

Table 11.1-2 Study Day and Visit Windows for Patient Diary Entries (PGI-I, PGI-S and 'Word of the Day')			
Week	Target Day a	Study Day Interval a	
1	2	2-7	
2	9	8-14	
3	16	15-21	
4	23	22-28	
5	30	29-35	
6	37	36-42	
7	44	43-49	
8	51	50-70 b	

<sup>a Relative to the date of 1st use of open-label brexpiprazole.

#### 11.2 Scales: Rules for Scoring and Handling of Missing Data

#### 11.2.1 Inventory of Depressive Symptomatology Self-Report (IDS-SR)

IDS-SR is utilized to assess core diagnostic depressive symptoms as well as the atypical and melancholic symptom features of MDD. The IDS-SR consists of 30 items, all rated on a 0 to 3 scale with 0 being the "best" rating and 3 being the "worse" rating. Besides item 9, two sub-items 9A and 9B exist, with possible scores of 1, 2 or 3 for item 9A, and 0 or 1 for item 9B. The scores for these two sub-items are not included in the calculation of the total score. Item 11 or item 12 should be completed but not both, and similarly, item 13 or item 14 should be completed but not both. Should items 11 and 12 be rated both, then the maximum of the two scores will be used. The same approach will be used for handling items 13 and 14.

The IDS-SR Total Score is the sum of ratings of 28 item scores. The possible IDS-SR Total Score ranges from 0 to 84. The IDS-SR Total Score will be un-evaluable if less than 23 of the 28 items are recorded. If the number of items recorded is at least 23 and at most 27, the IDS-SR Total Score will be the mean of the recorded items multiplied by 28 and then rounded to the first decimal place.

The IDS-SR symptom severity is rate using the following categories based on IDS-SR total Score: 0-13: None, 14-25: Mild, 26-38: Moderate, 39-48: Severe, and 49-84: Very severe.

The IDS-SR related scales are assessed at each scheduled visit.

<sup>a Relative to the date of 1st use of open-label brexpiprazole; If more than one observation falls within a particular study day interval, then the last observation within that interval is used.

<sup>b Evaluations occurring more than seven days after the last open-label brexpiprazole date will be excluded.

#### 11.2.2 IDS-SR-10-Engagement

The IDS-SR-10-engagement is the sum of ratings of the selected 10 item scores by clinician. It includes item 8 - Response of your mood to good or desired events, item 15 -Concentration/decision making, item 16 - View of myself, item 17 - View of my future, item 19 - General interest, item 20 - Energy level, item 21 - Capacity for pleasure or enjoyment (excluding sex), item 22 - Interest in sex (please rate interest, not activity), item 23 - Feeling slowed down, and item 29 - Interpersonal sensitivity. The possible IDS-SR-10-engagement ranges from 0 to 30. The IDS-SR-10 engagement will be unevaluable if less than 8 of the 10 items are recorded. If 8 or 9 of the 10 items are recorded. the IDS-SR-10 engagement will be the mean of the recorded items multiplied by 10 and then rounded to the first decimal place.

The weighted IDS-SR-10 engagement is a weighted average of the above selected 10 items by clinician. According to the mean relevance rating, the weights are shown in Table 11.2.2-1. If 1 or 2 items are missing, the average of the remaining items will be used to replace those missing items, and the weights below will then be applied for calculation.

Table 11.2.2-1 Weights for Calculating the weighted IDS-SR-10 Engagement		
IDS-SR Item	Weight	
Items 20, 21	0.109 each	
Items 8, 15	0.106 each	
Item 19	0.103	
Item 17	0.1	
Item 16, 23	0.097 each	
Item 22	0.088	
Item 29	0.085	

#### 11.2.3 IDS-SR Patient-Selected Engagement Items

The IDS-SR patient-selected engagement items is the sum of rating of the selected 10 items score by patients. It includes item 5 - Feeling sad, item 8 - Response of your mood to good or desired events, item 10- The quality of your mind, item 15 -

Concentration/decision making, item 16 - View of myself, item 17 - View of my future, item 19 - General interest, item 20 - Energy level, item 21 - Capacity for pleasure or enjoyment (excluding sex), and item 23 - Feeling slowed down. The possible IDS-SR patient-selected engagement items range from 0 to 30. The IDS-SR patient-selected engagement items will be un-evaluable if less than 8 of the 10 items are recorded. If 8 or

9 of the 10 items are recorded, the IDS-SR patient-selected engagement items will be the mean of the recorded items multiplied by 10 and then rounded to the first decimal place.

The sum of the common 8 IDS-SR item scores selected by both clinician and patients will be also calculated. If 1 of 8 items is missing, then the total score will be un-evaluable.

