### 5.2 Handling of Missing Data

IDS-SR is utilized as the primary efficacy measurement to assess core diagnostic depressive symptoms as well as the atypical and melancholic symptom features of MDD. The IDS-SR consists of 30 items, all rated on a 0 to 3 scale with 0 being the "best" rating and 3 being the "worse" rating. Besides item 9, two sub-items 9A and 9B exist, with possible scores of 1, 2 or 3 for item 9A, and 0 or 1 for item 9B. The scores for these two sub-items are not included in the calculation of the total score. Item 11 or item 12 should be completed but not both, and similarly, item 13 or item 14 should be completed but not both. Should items 11 and 12 be rated both, then the maximum of the two scores will be used. The same approach will be used for handling items 13 and 14.

The IDS-SR Total Score is the sum of ratings of 28 item scores. The possible IDS-SR Total Score ranges from 0 to 84. The IDS-SR Total Score will be un-evaluable if less than 23 of the 28 items are recorded. If the number of items recorded is at least 23 and at most 27, the IDS-SR Total Score will be the mean of the recorded items multiplied by 28 and then rounded to the first decimal place.

The IDS-SR-10-engagement is the sum of ratings of the selected 10 item scores, including item 8 - Response of your mood to good or desired events, item 15 - Concentration/decision making, item 16 - View of myself, item 17 - View of my future, item 19 - General interest, item 20 - Energy level, item 21 - Capacity for pleasure or enjoyment (excluding sex), item 22 - Interest in sex (please rate interest, not activity),

item 23 - Feeling slowed down, and item 29 - Interpersonal sensitivity. The possible IDS-SR-10-engagement ranges from 0 to 30. The IDS-SR engagement score will be unevaluable if less than 8 of the 10 items are recorded. If 8 or 9 of the 10 items are recorded, the IDS-SR engagement score will be the mean of the recorded items multiplied by 10 and then rounded to the first decimal place.

The observed-cases (OC) data set will consist of actual observations recorded at each scheduled visit during the open-label treatment phase, and no missing data will be imputed. MMRM analysis will be performed on the OC dataset.

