#### 8.2 Other Efficacy Endpoint Analysis

The other efficacy endpoints are as follows. All of them will be evaluated at a nominal 0.05 level (2-sided) without adjusting for multiplicity on Efficacy Sample:

[figure not shown]
- 1) Change from baseline to Weeks 2 and 4 in IDS-SR-10-engagement
- 2) Change from baseline to Weeks 2 and 4 in IDS-SR Total score
- 3) Change from baseline to Weeks 2, 4, and 8 in IDS-SR patient-selected engagement items
- 4) Change from baseline to Weeks 2, 4, and 8 in IDS-SR engagement items selected by both clinicians and patients.
- 5) Change from baseline to Weeks 2, 4, and 8 in CGI-S score
- 6) CGI-I score at Weeks 2, 4, and 8
- 7) Change from baseline to Weeks 4 and 8 in SDS Mean score and SDS individual item scores
- 8) Change from baseline to Weeks 4 and 8 in WHODAS 2.0 short form score.
- 9) Change from baseline to Weeks 2, 4, and 8 in PHQ-9 score
- 10) Change from baseline to Weeks 2, 4, and 8 in GAD-7 score
- 11) PGI-I score at each timepoint (ie, being measured weekly at home)

- 12) PGI-I response rate at each timepoint (ie, being measured weekly at home), where response is defined as a PGI-I score of 1 or 2 (very much improved or much improved)
- 13) Time to first PGI-S response, where response is defined as a reduction of 2 points in PGI-S score from baseline.

Endpoint (1) - (5), (7) - (10) will be analyzed by fitting the same MMRM model described in the primary analysis on OC dataset. Endpoints (6) and (11) will be analyzed using one-sample t-test on LOCF dataset, with the null hypothesis of no change in each of the endpoints. The point estimate with 95% CI will be provided for endpoint (12) using normal approximation on LOCF dataset. Endpoint (13) will be evaluated by time-to-event analysis with Kaplan-Meier curve on OC dataset. The time origin for measuring this event time is the date of the first dose of open-label brexpiprazole. The event date will be the date when a reduction of 2 points in PGI-S score from baseline is achieved.

Version Date: 29 Jun 2022

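### SAP 11.2.3 voids the 8-item common engagement score (endpoint 4) for one missing item, while the other IDS-SR scores from the same form are prorated, and no reason is given

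*SAP*

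**What the plan says.** SAP 11.2.3 defines the score: "The sum of the common 8 IDS-SR item scores selected by both clinician and patients will be also calculated". Its missing-item rule follows at once: "If 1 of 8 items is missing, then the total score will be un-evaluable".

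The other IDS-SR scores are treated differently:

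- **IDS-SR-10-engagement (co-primary 1), SAP 5.2 and 11.2.2:** "The IDS-SR engagement score will be unevaluable if less than 8 of the 10 items are recorded". Above that threshold it is prorated: "If 8 or 9 of the 10 items are recorded, the IDS-SR engagement score will be the mean of the recorded items multiplied by 10".
- **Patient-selected 10-item score (endpoint 3), SAP 11.2.3:** "The IDS-SR patient-selected engagement items will be un-evaluable if less than 8 of the 10 items are recorded". It is prorated in the same way.
- **IDS-SR Total (co-primary 2), SAP 5.2 and 11.2.1:** "The IDS-SR Total Score will be un-evaluable if less than 23 of the 28 items are recorded". With 23 to 27 items it is prorated to 28.
- **Weighted IDS-SR-10, SAP 11.2.2:** one or two missing items are replaced by the average of the rest.

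Endpoint 4 in SAP 8.2 is "Change from baseline to Weeks 2, 4, and 8 in IDS-SR engagement items selected by both clinicians and patients". It belongs to the group that "will be analyzed by fitting the same MMRM model described in the primary analysis on OC dataset". Under SAP 5.1, membership of the Efficacy Sample depends on the Total and IDS-SR-10-engagement, not on the 8-item score.

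**The concern.** The eight common items all lie inside both 10-item lists. The SAP accepts a score made of these eight plus two others when two items are missing, yet rejects the eight alone when one is missing. The stricter rule can only cost endpoint 4 data, because one skipped common item leaves the Total and both 10-item scores evaluable.

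Two things are at stake. First, responses already collected are discarded. Second, anyone who reads endpoint 4 beside co-primary 1, to see whether the engagement result holds on the items both groups chose, may be reading the two on different observed sets. A skip at baseline matters most. The IDS-SR is first scheduled at the baseline visit (Protocol Table 1.3-1), so there is no scheduled earlier form to fall back on, and the patient then has no endpoint 4 change at any visit.

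**Working it through.** **Plan's own figures.** The plan states none for the 8-item score. Its power statement concerns the co-primaries only and reproduces. With 100 completers and a two-sided 0.05 one-sample t test, a change of -5 (SD 13.5) in the Total gives 95.6% power, and -2.5 (SD 6.5) in IDS-SR-10-engagement gives 96.8%. Power for both is at least 95.6 + 96.8 - 100 = 92.4%. Enrolment is 100/(1 - 0.25), rounded up to 134. The 8-item rule enters none of this.

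**Items.** The clinician list is 8, 15, 16, 17, 19, 20, 21, 22, 23, 29. The patient list is 5, 8, 10, 15, 16, 17, 19, 20, 21, 23. The overlap is 8, 15, 16, 17, 19, 20, 21, 23, which is eight items.

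**One common item skipped, the rest complete.**

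| Score | Items recorded | Tolerance in SAP | Result |
|---|---|---|---|
| IDS-SR Total | 27 of 28 | 5/28 = 18% missing | prorated |
| IDS-SR-10-engagement | 9 of 10 | 2/10 = 20% missing | prorated |
| Patient-selected 10 | 9 of 10 | 2/10 = 20% missing | prorated |
| 8 common items | 7 of 8 (12.5% missing) | none | void |

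**Size.** The per-item missing rate q is an assumption, taken as equal and independent across items and visits.

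- 8-item form void: v = 1 - (1 - q)^8.
- 10-item form void: P(Bin(10, q) ≥ 3).
- Week 8 change lost (baseline or Week 8 form void): 1 - (1 - v)^2.
- Patient absent from the endpoint 4 MMRM (baseline void, or all three post-baseline forms void, for a patient who attends every visit): 1 - (1 - v)(1 - v^3).
- 8-item form void under a 7-of-8 rule: P(Bin(8, q) ≥ 2).

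Example at q = 1%: 0.99^8 = 0.9227, so v = 7.7%. The Week 8 change is lost in 1 - 0.9227^2 = 14.9%. A patient is absent with probability 1 - 0.9227 × (1 - 0.0773^3) = 7.8%.

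| Assumed q | 8-item form void | 10-item form void | Week 8 change lost | Patient absent from MMRM | 8-item form void, 7-of-8 rule |
|---|---|---|---|---|---|
| 0 | 0 | 0 | 0 | 0 | 0 |
| 0.1% | 0.8% | <0.01% | 1.6% | 0.8% | <0.01% |
| 0.5% | 3.9% | <0.01% | 7.7% | 3.9% | 0.07% |
| 1% | 7.7% | 0.01% | 14.9% | 7.8% | 0.27% |
| 2% | 14.9% | 0.09% | 27.6% | 15.2% | 1.0% |

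The Week 8 column counts missing change scores, not missing patients. In the MMRM a void post-baseline form removes that visit only, and the patient's other visits still contribute. The MMRM column is the one that counts patients.

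**The case against.** The rule is explicit and unambiguous, and it applies to one of 13 other endpoints tested at a nominal 0.05 level. Complete-item scoring is not foreign to this SAP: the SDS mean needs all its items apart from a non-applicable work item, and no proration is stated for the PHQ-9 or GAD-7. No general 80% standard is written down. The protocol describes electronic capture (10.1.6.2) and asks staff to encourage full completion of the IDS-SR (8.1.1), so item non-response may be very low. For a given q, skips that cluster on the same forms void fewer 8-item forms than independence implies, and more 10-item forms, so the contrast in the table leans towards the unfavourable end. Endpoint 3 also omits clinician-only items 22 and 29 and is prorated under the same rule as co-primary 1, so a reading without those two items under matching rules already exists.

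Most of this stands, and it limits the size of the point. It does not explain why one score from a form should be handled differently from every other score on that form. Nor do the documents say that items cannot be skipped. The SAP writes proration rules for this same questionnaire, and Protocol 10.1.6.2 also refers to source documentation captured on paper and transcribed.

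**Conclusion.** The inconsistency is real and unexplained, and its importance is minor. The data loss is conditional: negligible at an item-missing rate near 0.1%, material for endpoint 4 from about 1%, and nil if every item must be entered. All figures rest on assumed, independent item-missing rates.

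A reader might infer more, and the documents do not support it:

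- That endpoint 4 will lose patients. No item-missing rate is given, so it can lose them, but the plan does not show that it will.
- That every void form costs a patient. Only a void baseline, or void scores at all post-baseline visits, does so.
- That the plan compares endpoint 4 with the co-primary on mismatched patients. The readable text tests endpoint 4 on its own and plans no such contrast. SAP numbering passes from 8.2 to 8.4, but a comparison cannot be presumed from a gap.
- That the trial's conclusion is at risk. Success depends only on the two co-primaries. Their power and type I error, and Efficacy Sample membership, do not use the 8-item score.

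**What to change.** In SAP 11.2.3, replace the complete-item sentence with this rule: *the 8-item score is evaluable only when at least 7 of its 8 items are present; with exactly 7, take their mean times 8, to one decimal place.* This tolerates 12.5% missing, which is tighter than the 20% accepted for the 10-item scores. Also report the number of evaluable 8-item scores at baseline and at Weeks 2, 4 and 8. If the sponsor has a reason to require all eight items, it should state that reason and still report those counts.

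The cost is one SAP sentence, one line of code and one row of counts, with no new data. The small downside is that a few scores will rest on seven items.

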#### 11.2.4 Patient Health Questionnaire-9 (PHQ-9)

The PHQ-9 is a standardized, self-administered rating scale that assesses the severity of depressive symptoms. The scale consists of 9 items, representing the 9 criteria upon which the diagnosis of DSM-5 depressive disorders is based. Each item is rated from 0 (not at all) to 3 (nearly every day). The total score ranges from 0 to 27. A higher score on the PHQ-9 represents a higher severity of depressive symptoms. The PHQ-9 is assessed at screening and each scheduled visit.

#### 11.2.5 Generalized Anxiety Disorder-7 (GAD-7)

The GAD-7 is a self-reported questionnaire designed to assess anxiety in subjects. The scale contains 7 items and each item is rated from 0 (not at all) to 3 (nearly every day). The total score ranges from 0 to 21. A higher score on the GAD-7 represents greater anxiety symptomatology. The GAD-7 is assessed at each scheduled visit.

#### 11.2.6 World Health Organization Disability Assessment Schedule 2.0 (WHODAS 2.0) Short Form Questionnaire

The WHODAS 2.0 short form is a 12-item self-assessment questionnaire to assess a patient's activity limitations and participation restrictions (ie, disability) across 6 domains of life: cognition (understanding and communicating), mobility (moving and getting around), self-care (hygiene, dressing, eating, staying alone), getting along (interacting with others), life activities (domestic responsibilities, leisure, work and school), and participation (community and society). Each item is rated from 1 (none) to 5 (extreme or cannot do). To calculate WHODAS 2.0 short form score, a single sum method of scoring all 12 items identified in the manual of WHODAS 2.0^2 is used. Therefore, the short form score ranges from 5 (no disability) to 60 (complete disability). When only one item is missing, the simple approach mentioned in the manual of WHODAS 2.0^2 is used to handle missing data. This method should not be used if more than one item is missing. In situation where one or two items are missing, it will be handled as described in the manual of WHODAS 2.0. The WHODAS 2.0 short form is assessed at baseline, Weeks 4 and 8.

### 11.2.7 Sheehan Disability Scale (SDS)

The Sheehan Disability Scale (SDS) is a self-rated instrument used to measure the effect of the patient's symptoms on work/school, social life, and family/home responsibilities. For each of the three items, scores range from 0 through 10. The number most representative of how much each area was disrupted by symptoms is marked along the line from 0 = not at all, to 10 = extremely. For the work/school item, no response was to be entered if the patient did not work or go to school for reasons unrelated to the disorder and a response therefore not being applicable. The Mean SDS Score will be calculated over the three item scores. All three item scores need to be available with the exception of the work/school item score when this item is not applicable. The SDS is assessed at baseline, Weeks 4 and 8.

## 11.2.8 Clinical Global Impression - Severity of Illness Scale (CGI-S)

The severity of agitation for each subject will be rated using the Clinical Global Impression- Severity of Illness Scale (CGI-S). To perform this assessment, the investigator (or designee) will answer the following question: "Considering your total clinical experience with this particular population, how mentally ill (as related to agitation) is the subject at this time?" Response choices are 0 = not assessed; 1 = normal, not at all ill; 2 = borderline mentally ill; 3 = mildly ill; 4 = moderately ill; 5 = markedly ill; 6 = severely ill; and 7 = among the most extremely ill subjects. The score 0 (not assessed) will be set to missing. The CGI-S is therefore a 7-point scale from 1 through 7. The CGI-S is assessed at each scheduled visit.

### 11.2.9 Clinical Global Impression - Improvement (CGI-I)

The efficacy of trial treatment will be rated for each patient using the Clinical Global Impression - Improvement (CGI-I) scale. The rater or investigator will rate the patient's total improvement whether or not it is due entirely to drug treatment. Response choices include: 0 = not assessed, 1 = very much improved, 2 = much improved, 3 = minimally improved, 4 = no change, 5 = minimally worse, 6 = much worse, and 7 = very much worse. The score 0 (not assessed) will be set to missing. The CGI-I is therefore a 7-point scale from 1 through 7. The CGI-I is assessed at Weeks 2, 4, and 6.

